10.6.4.3. Blood Pressure Endpoints

Blood Pressure Endpoints
Pre- and Post- Dialysis BP

 For subjects undergoing dialysis in-clinic, both pre- and post- dialysis BP values will be measured. Unless otherwise specified, for summaries and analyses of BP values, the post-dialysis BP values for subjects undergoing dialysis in-clinic will be used.
End of Treatment BP Value

 See Section 10.6.1

Blood Pressure Endpoints
Mean Arterial Pressure (MAP)

 MAP = $[(2*DBP)+SBP]/3$
Blood Pressure Exacerbations

 BP exacerbations will be defined as (≥ 25 mmHg increase from baseline or SBP ≥ 180 mmHg or DBP ≥ 15 mmHg increase from baseline or DBP ≥ 110 mmHg) and grouped by type as follows: 
 BP exacerbations 
 SBP exacerbations 
 ≥ 25 mmHg increase from baseline or SBP ≥ 180 mmHg 
 SBP ≥ 180 mmHg and baseline SBP < 180 mmHg (including subjects with a missing baseline SBP) SBP ≥ 180 mmHg and baseline SBP ≥ 180 mmHg DBP exacerbations 
 ≥ 15 mmHg increase from baseline or DBP ≥ 110 mmHg 
 DBP ≥ 110 mmHg and baseline DBP < 110 mmHg (including subjects with a missing baseline DBP) DBP ≥ 110 mmHg and baseline DBP ≥ 110 mmHg
Notes:

 BP values used to assess BP exacerbations must be on-treatment (see Section 10.4.1), unless otherwise specified. BP values used to assess BP exacerbations can be scheduled or unscheduled. For visits where BP is measured in triplicate, the average of the 3 BP values will be used to assess BP exacerbations. For subjects who start in-clinic dialysis during the study, BP exacerbations identified using post-dialysis BP values will be used in summaries and analyses of BP exacerbations, unless otherwise specified. Subjects with multiple exacerbation events on the same calendar date for each type defined above are considered to have one exacerbation event for event counts by type. For example, a subject with a SBP and a DBP exacerbation on the same date would count in each of the SBP and DBP types, but would only count as one BP exacerbation event in the total BP exacerbation type.
Blood Pressure Exacerbation Event Date

 Date of BP exacerbation
On-Treatment BP Medication

 See Section 10.4.1 for treatment states for concomitant medications.
General

 Censored time (days) = last non-zero dose date– treatment start date + 1 BP exacerbation person years = (cumulative total of censoring time for all subjects) / 365.25 BP exacerbation event incidence rate (per 100 person years) = $(100 * \text{number of BP exacerbations}) / \text{BP exacerbation person years}$

Blood Pressure Endpoints
Changes in Blood Pressure Medications

 • No change: no new anti-hypertensive records since baseline (day before randomized treatment start date) and no change to anti-hypertensive records since baseline until date of visit while on randomized treatment. • Increase: addition of new anti-hypertensive records for any reason or a change with a primary reason for changing dose/frequency or stopping of ‘increased to...’ since baseline until date of visit while on randomized treatment • Decrease: discontinuation of an anti-hypertensive record with primary reason for change starting with “discontinuedor” or a change with a reason of ‘Decreased due to...’ since baseline until date of visit while on randomized treatment • Switch = change with a reason of ‘switched to another agent..’ since baseline until date of visit while on randomized treatment
Cumulative Changes in Blood Pressure Medications

 • For the summary of cumulative changes excluding “Once only” and “PRN” records, cumulative change will be counted from the date of first randomized treatment to the Week 52 visit date while on randomized treatment. If a new anti-hypertensive medication is added during this time, it will be counted as one change. If the medication also stops during this period, then it will count as two changes (one change due to starting, and one change due to stopping). The cumulative number of changes will be calculated by adding up the changes for all records during this time period. The same steps will be repeated for the period starting from the date of first randomized treatment to End of Treatment • For the summary of cumulative changes for “Once only” records only, cumulative change will be counted from the date of first randomized treatment to the Week 52 visit date while on randomized treatment. Since “Once only” doses will have same start and stop dates, a new anti-hypertensive medication record during this period will be counted as one change. As “once only” doses are likely administered to control BP during dialysis, so they are considered part of a single titration regimen, hence multiple “once only” records on the same date will be counted as one change. The same steps will be repeated for the period starting from the date of first randomized treatment to End of Treatment

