
 • To further compare daprodustat and darbepoetin alfa on Hgb variability 	
 • Hgb observed and change from baseline across all visits to end of treatment • % of time Hgb is above, within and below the range of 10-11.5 g/dL during EP and MP • Number (%) of subjects with mean Hgb above, within and below the Hgb analysis range during EP and at the end of treatment • Number (%) of subjects with a Hgb <7.5 g/dL during the EP and MP • Number of times Hgb <7.5 g/dL during the EP and MP • Number (%) of subjects with a >1g/dL increase in Hgb over 2 weeks (assessed at Week 2 and Week 4) or a >2 g/dL increase in Hgb within any 4 week period from Week 4 to Week 52 • Number (%) of subjects with a >1g/dL decrease in Hgb over 2 weeks (assessed at Week 2 and Week 4) or a >2 g/dL decrease in Hgb within any 4 week period from Week 4 to Week 52 • N (%) of subjects with a Hgb value \geq 12 g/dL during the EP and MP • Number of times Hgb \geq 12 g/dL during the EP and MP • % of time Hgb \geq 12 g/dL during the EP and MP

 • To compare daprodustat to darbepoetin alfa on measures of iron parameters 	
 • Observed and change from baseline in hepcidin, ferritin, TSAT, total iron, TIBC across all visits to end of treatment • Average quarterly ferritin • Average quarterly TSAT • N (%) of subject who met iron management criteria

 • To further compare daprodustat to darbepoetin alfa on BP and BP medication changes 	
 • Observed and change from baseline in SBP, DBP and MAP by visit • Number of BP medications per subject by visit • Change from baseline in the number of BP medications per subject by visit • N (%) of subjects who had no change, an increase or a decrease in the dosage or number of BP medications from baseline by visit

 • To compare daprodustat to darbepoetin alfa on the need for RBC and whole blood transfusions 	
 • Number (%) of subjects who receive at least one RBC or whole blood transfusions by Week 52 and by end of treatment • Number of RBC and whole blood transfusions per 100 patient years

Objectives	Endpoints
	
 Number of RBC and whole blood units per 100 patient years

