8.2.3.2. Planned Exploratory Safety Display Details*Blood Pressure*

The last on-treatment BP parameter change from baseline value (SBP, DBP, and MAP) recorded prior to the first change in BP medications will be summarized using mean, standard deviation, minimum, P25, median, P75, and maximum by treatment group. The first change in blood pressure medication occurs at the earliest time a new anti-hypertensive medication is administered or if the dose or frequency of an existing blood pressure medication is changed for any reason (increased, decreased, discontinued, or switched to another agent) in any anti-hypertensive medication, except medication records with frequencies of “Once only” and “PRN.”

Number of BP medications per subject while the subject was on treatment will be summarized using mean, standard deviation, minimum, P25, median, P75, and maximum for each scheduled visit by treatment group. Number of BP medications for each subject at baseline is defined as the number of medications taken on the day before randomized treatment start date. For end of treatment, it is defined as the number of medications taken on last non-zero dose date + 1 day. The number of BP medications at all other nominal visits is defined as the number of medications taken on the day of the visit.

Medication records with frequencies of “Once only” and “PRN” will be excluded from this summary.

Change from baseline in the number of BP medications per subject while the subject was on treatment will be summarized using mean, standard deviation, minimum, P25, median, P75, and maximum for each scheduled visit by treatment group. The number of BP medications at baseline, end of treatment and all other nominal visits will be defined as described in the previous paragraph. Medication records with frequencies of “Once only” and “PRN” will be excluded from this summary.

Additionally, the number and percentage of subjects who had no change, at least one change, an increase, a decrease or a switch in the dosage or number of BP medications from baseline while the subject was on treatment will be summarized for each scheduled post-baseline visit by treatment group (see Section 10.6.4 for details of classifying BP medication changes). Medication records with frequencies of “Once only” and “PRN” will be excluded from this summary.

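### The rule for an increase in BP medication counts any new antihypertensive record, so a one-for-one switch of agent is scored as both Switch and Increase

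*SAP*

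**What the plan says.** The endpoint in SAP section 2.2 is the number and percentage of subjects with no change, or with "an increase or a decrease in the dosage or number of BP medications from baseline by visit". Section 8.2.3.2 widens the display to "an increase, a decrease or a switch in the dosage or number of BP medications", plus a row for at least one change, and refers to section 10.6.4 for the classification.

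The definitions in section 10.6.4.3 are:

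- "No change: no new anti-hypertensive records since baseline", together with no change to existing records.
- "Increase: addition of new anti-hypertensive records for any reason", or a change whose stated reason is an increase. The two parts are alternatives, so a new record is enough on its own.
- "Decrease: discontinuation of an anti-hypertensive record with primary reason for change starting with" the word for discontinued, or a change whose stated reason is a decrease.
- "Switch = change with a reason of" a switch to a different agent.

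Each category runs from baseline to the date of the visit, while on randomized treatment. Section 8.2.3.2 removes once-only and PRN records from this summary. Nothing else is carved out. Neither section ranks the categories, makes them exclusive or says that they may overlap.

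**The concern.** The table is meant to show the direction in which BP treatment moved. Increase is triggered by the existence of a record, whereas Switch is triggered by a reason and Decrease mainly so. A switch normally produces a new record for the replacement agent, and that record meets the Increase rule although the subject takes the same number of agents as before.

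This bears on how the BP results are read. The background in section 10.14 notes that BP elevation caused by ESAs often leads to more antihypertensive treatment. The BP models in section 8.2.2.2 do not adjust for BP medication. The sub-study comparison of subjects needing an increase or decrease in antihypertensives is marked as not done in section 10.14.1.2. The main-study summaries are therefore the only planned between-arm display of BP-treatment change by direction.

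**Working it through.** The plan gives no figure to reproduce. The check is to apply the section 10.6.4.3 rules as written to single record histories between baseline and a visit, and to compare the result with the change in the counted number of regular BP medications.

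| Case | Increase | Decrease | Switch | Change in number |
|---|---|---|---|---|
| 1. Agent added to existing therapy | Yes | No | No | +1 |
| 2. Agent discontinued, not replaced | No | Yes | No | -1 |
| 3. Agent A stopped as a switch; agent B entered as a new regular record by the visit | **Yes** | No | Yes | -1 + 1 = 0 |
| 4. As case 3, but B is PRN or once-only, or has not started by the visit | No | No | Yes | -1 |
| 5. Dose lowered, no new record opened | No | Yes | No | 0 |

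Cases 1, 2 and 5 come out as the endpoint intends. Case 3 does not: the number is unchanged, yet the subject is in the Increase column. The rule does not look at dose or intensity across agents, so it cannot tell a neutral switch from a step up.

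The error has one direction. In case 3 the start of B satisfies the new-record part of Increase. The stop of A carries a switch reason, which is neither of the two reasons that make a Decrease. A switch thus adds to Increase and never to Decrease.

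It also persists. Because the categories accumulate from baseline, a subject in case 3 stays an Increase at every later on-treatment visit.

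The effect on the comparison can be written down but not evaluated. For a given arm and visit, let *p* be the proportion with a genuine increase and *s* the proportion with a case 3 switch and no genuine increase. Then:

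- reported Increase = *p* + *s*;
- reported difference between arms = (difference in *p*) + (difference in *s*).

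A subject who switches and also truly escalates is already in *p* and adds no error. If *s* is equal in both arms, the absolute difference is unaffected, both percentages are too high, and their ratio is pulled towards 1. If *s* differs, the arm with more switching appears to need more BP treatment. The document gives no value for *s*.

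Section 8.2.3.2 also plans, within the cumulative summary, a count of subjects by reason (increase, decrease, switch). No separate definition is given there. If the same definitions are used, the overlap carries over to that row.

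**The case against.** The best defence is that other displays show net change. Section 8.2.3.2 summarises how many BP medications each subject takes at each visit and the change in that number from baseline. A completed one-for-one switch nets to zero in both. It also summarises the last BP value before the first medication change. Switch and Decrease appear beside Increase, so a careful reader may suspect overlap. The endpoint is exploratory with no planned test. All of this stands and limits the consequence. It does not make the Increase column correct, and a count of drugs cannot show dose escalation.

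A second defence is that a new record was meant to signify a new drug. The separate part for changes whose reason is an increase would be redundant if every dose change opened a countable record, and section 8.2.3.2 distinguishes a new medication from a change to an existing one. This is a fair reading, but it does not rescue case 3, because the replacement agent is a new drug.

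Three stronger readings are tempting and are not supported:

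- **Every dose reduction is also scored as an Increase.** That would need the eCRF to close the old record and open a new one at the lower dose. The SAP does not show this, and the two-part definition of Increase suggests otherwise.
- **The cumulative count has the same fault.** Section 10.6.4.3 says of an added drug: "If the medication also stops during this period, then it will count as two changes". That count has no direction, so a stop plus a start scoring two misclassifies nothing as escalation.
- **The inflation can be put at some multiple of the truth.** Any such figure needs an assumed mix of additions, switches and reductions, for which the document offers no basis.

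**Conclusion.** The rule is wrong as written for one common pattern. A switch whose replacement is a regular record started by the visit is counted as both Switch and Increase although the number of BP medications did not rise. Only the Increase column is inflated. This follows from the wording and needs no assumption about the eCRF beyond the replacement agent having its own record. It does not apply to every switch, as case 4 shows.

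The size cannot be derived from the SAP. The reach is limited to exploratory, on-treatment, descriptive tables. No co-primary, principal secondary or BP model uses the category. It should be corrected before unblinding because the table reports a direction of BP treatment and the error is systematic, but no main conclusion of the trial depends on it.

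**What to change.** Amend section 10.6.4.3 as follows:

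1. Limit the new-record part of Increase to a new antihypertensive agent that does not replace one stopped with a switch reason. Exclude continuation records of the same agent unless the recorded reason is an increase.
2. Classify a switch once, from the reason on the old record.
3. State how old and new records are paired when dates are partial. Section 10.7.2.1 moves a partial start to the first of the month (or January) and a partial stop to the end of the month (or December). With only the day missing, a switch within June would be dated as a start on 1 June and a stop on 30 June, which are 29 days apart, so pairing on the same or adjacent dates would fail.
4. State whether a subject may appear in more than one category at a visit, and footnote the tables accordingly.

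The cost is a few lines of SAP text and a record-linking step in programming. No new data are needed. The cumulative count can stay as it is.

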10.6.4.4. Adverse Events

Adverse Events
AEs of Special Interest

Adverse events of special interest are classified as follows:
 
 • Thrombosis and/or tissue ischemia secondary to excessive erythropoiesis • Cardiomyopathy • Pulmonary artery hypertension • Cancer-related mortality and tumor progression and recurrence • Esophageal and gastric erosions • Proliferative retinopathy, macular edema, choroidal neovascularization • Exacerbation of rheumatoid arthritis • Worsening of hypertension

Adverse Events

Potential AESIs will be identified through a pre-defined terms of interest process in which pre-defined lists of AE preferred terms corresponding with each AESI will be used to identify events considered to be potential AESIs. Sites will be prompted via query to complete any necessary additional information for these AESIs in the eCRF.

For the category of thrombosis and/or tissue ischemia secondary to excessive erythropoiesis, after the terms of interest list has been applied, the additional Hgb criteria described below will be applied to identify only those events that are considered to be secondary to excessive erythropoiesis as meeting the AESI definition for thrombosis and/or tissue ischemia secondary to excessive erythropoiesis.

Thrombosis and tissue ischemia events will be considered to be secondary to excessive erythropoiesis if during the window of [AE start date – 30 days, AE start date +15 days] any one of the following 3 events occurs:

- Any Hgb value \geq 13 g/dL (measured pre-dialysis)
- Hgb increase $>$ 2 g/dL over 2 weeks (+1 week)
 - Note: for programming purposes, a +1 week window is applied, corresponding to the allowable visit window, to look for increases $>$ 2 g/dL over 3 weeks
- Hgb increase $>$ 4 g/dL over 4 weeks (+1 week)
 - Note: for programming purposes, a +1 week window is applied, corresponding to the allowable visit window, to look for increases $>$ 4 g/dL over 5 weeks

To identify Hgb increases that meet the increase criterion above, all Hgb values taken within [AE start date – 58 days, AE start date + 15 days] will be identified. This corresponds to identifying Hgb values that occurred 4 weeks before the [AE start date – 30 days, AE start date +15 days] window of interest. HemoCue Hgb and central laboratory Hgb values will then be evaluated separately to identify increases, so that HemoCue and central laboratory Hgb values are not compared to each other to identify an increase.

For HemoCue Hgb and separately for central laboratory Hgb values, if there is a Hgb value (or daily Hgb average) within the [AE start date – 30 days, AE start date +15 days] window and an earlier Hgb value (or daily Hgb average) that is within the larger [AE start date – 58 days, AE start date + 15 days] window, and the amount of time between the two Hgb values is:

- Between 1 day and 3 weeks, inclusive, then the Hgb values will be compared to determine if there has been a Hgb increase $>$ 2g/dL.
- Between 15 days and 5 weeks, inclusive, then the Hgb values will be compared to determine if there has been a Hgb increase $>$ 4g/dL.

Unscheduled Hgb values will also be used in the assessment of secondary to excessive erythropoiesis following the guidance specified in Section [10.6.3](#) for unscheduled Hgb values and

Adverse Events

multiple Hgb values on the same date.

Pre-defined Lists of AE Preferred Terms Corresponding with Each AESIThrombosis and/or tissue ischemia secondary to excessive erythropoiesis

- Narrow SMQ: Embolic and thrombotic events, arterial
- Narrow SMQ: Embolic and thrombotic events, venous
- Narrow SMQ: Embolic and thrombotic events, vessel type unspecified and mixed arterial and venous
- Broad SMQ: Thrombophlebitis
- Additional Preferred Terms:
 - Vascular access site occlusion
 - Vascular access site complication
 - Retinal vascular occlusion
 - Administration site ischaemia
 - Anterior segment ischaemia
 - Application site ischaemia
 - Biliary ischaemia
 - Bone marrow ischaemia
 - Brain stem ischaemia
 - Catheter site ischaemia
 - Cerebellar ischaemia
 - Cerebral ischaemia
 - ECG signs of myocardial ischaemia
 - Gastrointestinal ischaemia
 - Graft ischaemia
 - Hepatic ischaemia
 - Implant site ischaemia
 - Infusion site ischaemia
 - Injection site ischaemia
 - Intestinal ischaemia
 - Ischaemia
 - Macular ischaemia
 - Medical device site ischaemia
 - Myocardial ischaemia
 - Peripheral ischaemia
 - Renal ischaemia
 - Retinal ischaemia
 - Spinal cord ischaemia
 - Stoma site ischaemia
 - Subendocardial ischaemia
 - Uterine ischaemia
 - Vaccination site ischaemia
 - Vestibular ischaemia
 - Cerebral small vessel ischaemic disease
 - Colitis ischaemic
 - Delayed ischaemic neurological deficit
 - Hypoxic-ischaemic encephalopathy
 - Ischaemic cardiomyopathy
 - Ischaemic cerebral infarction
 - Ischaemic contracture of the left ventricle
 - Ischaemic enteritis
 - Ischaemic gastritis
 - Ischaemic heart disease prophylaxis
 - Ischaemic hepatitis
 - Ischaemic limb pain
 - Ischaemic mitral regurgitation
 - Ischaemic nephropathy
 - Ischaemic neuropathy
 - Ischaemic pancreatitis
 - Ischaemic skin ulcer
 - Ischaemic stroke
 - Necrosis ischaemic
 - Ocular ischaemic syndrome
 - Optic ischaemic neuropathy
 - Reversible ischaemic neurological deficit
 - Transient ischaemic attack

Cardiomyopathy

- Narrow SMQ: Cardiomyopathy

Pulmonary artery hypertension

- High Level Term: Pulmonary hypertension

Adverse Events

- Additional Preferred Terms:
 - Right ventricular dilatation
 - Right ventricular dysfunction
 - Right ventricular ejection fraction decreased
 - Right ventricular enlargement
 - Right ventricular failure
 - Right ventricular hypertrophy

Cancer-related mortality and tumor progression and recurrence

- Narrow SMQs:
 - Biliary malignant tumours
 - Biliary tumours of unspecified malignancy
 - Breast malignant tumours
 - Breast tumours of unspecified malignancy
 - Liver malignant tumours
 - Liver tumours of unspecified malignancy
 - Malignancy related conditions
 - Haematological malignant tumours
 - Non-haematological malignant tumours
 - Haematological tumours of unspecified malignancy
 - Non-haematological tumours of unspecified malignancy
 - Malignant lymphomas
 - Myelodysplastic syndrome
 - Oropharyngeal neoplasms
 - Ovarian malignant tumours
 - Ovarian tumours of unspecified malignancy
 - Prostate malignant tumours
 - Prostate tumours of unspecified malignancy
 - Tumour lysis syndrome
 - Skin malignant tumours
 - Skin tumours of unspecified malignancy
 - Uterine and fallopian tube malignant tumours
 - Uterine and fallopian tube tumours of unspecified malignancy
- Additional Preferred Terms:
 - Aplastic anaemia
 - Cytopenia
 - Myelosuppression
 - Pancytopenia
 - Aplasia pure red cell

Esophageal and gastric erosions

- High Level Terms:
 - Duodenal ulcers and perforation
 - Gastric ulcers and perforation
 - Gastrointestinal ulcers and perforation, site unspecified
 - Oesophageal ulcers and perforation
 - Peptic ulcers and perforation
- Additional Preferred Terms:
 - Haematemesis
 - Gastrointestinal haemorrhage
 - Upper gastrointestinal haemorrhage
 - Helicobacter duodenitis
 - Helicobacter gastritis
 - Melaena

Proliferative retinopathy, macular edema, choroidal neovascularization

Adverse Events

 • Broad SMQ: Retinal disorders 
Exacerbation of rheumatoid arthritis
 
 • High Level Term: Rheumatoid arthropathies • Additional Preferred Terms: 
 ○ Rheumatoid factor increased ○ Rheumatoid factor positive ○ Rheumatoid factor quantatative increased 
Worsening of hypertension
 
 • Narrow SMQ: Hypertension
Blood Pressure Events

BP events will be identified during the study via programmatic sweeps of AE and SAE terms entered into the eCRF (using the narrow SMQ for hypertension). AEs identified this way will require an additional BP Exacerbation eCRF page to be completed that characterizes the event as clinically significant and/or symptomatic.
 
In addition, subjects that experience BP values that meet the following criteria at any visit will also be considered to have a BP event and be required to complete the Blood Pressure Exacerbation eCRF page:
 
 • SBP: an increase from baseline of ≥ 25 mmHg or SBP ≥ 180 mmHg • DBP: an increase from baseline of ≥ 15 mmHg or DBP ≥ 110 mmHg

BP-related SAEs are those SAEs that have been identified via the BP Exacerbation eCRF page.

False Discovery Rate (FDR) Method and Procedure

The FDR method adjusts p-values within a group (SOC or preferred terms (PTs) within a SOC) based on the following:
 
 a) Order p-values from lowest to highest (1... m) b) Compute adjusted p-values, p', as follows 
 $p'(m) = p(m)$ i.e., the adjusted p-values for the highest p-value is the same as the highest p-value $p'(j) = \min(\{p'(j+1), m/j * p(j)\})$ for $j \leq m - 1$ 
The FDR procedure is applied at the system organ class (SOC) level and for each AE preferred term (PT) reported as Tier 2 events. The following steps will be undertaken in this procedure:
 
 1. Compute adjusted p-values for PTs within each SOC using the FDR method.

Adverse Events

 2. Order SOCs (small to large) according to the minimum FDR adjusted p-value observed for treatment differences across PTs within SOC. 3. Perform the FDR method on the minimum adjusted p-values from Step 2. 4. Select SOCs with FDR adjusted p-value from Step 3 <0.10. 5. Apply a single FDR adjustment to all unadjusted p-values belonging to all PTs from SOCs identified in Step 4. A threshold of FDR adjusted p-values <0.10 will be used to flag PTs that warrant further investigation. 
Note that 0.10 is recommended as a reasonable multiplicity adjustment for 0.05.

General Definitions

 • Post-Randomization last contact date for censoring (subjects not having AE) will be defined as the study completion date.

 • Treatment emergent last contact date for censoring (subjects not having AE) will be defined as follows: 
 ○ 1 day after the last non-zero dose date (last non-zero dose date + 1) for subjects not having treatment emergent AE and continuing on study past (last non-zero dose date + 1) ○ Last non-zero dose date for all other subjects

 • AE Patient Years: (Cumulative total of time to AE for subjects who have the AE + Cumulative total of censoring time for subjects without the AE) / 365.25 
 ○ For treatment emergent AEs, the start date of the patient years value for each subject should be the treatment start date. ○ For post-randomization AEs, the start date of the patient years value for each subject should be the randomization date. ○ For follow-up AEs, the start date of the patient years value for each subject should be 2 days after the last non-zero dose date (last non-zero dose date + 2).

 • Incidence Rate (per 100 patient years): $(100 * \text{Number of subjects with at least 1 AE}) / \text{AE person years}$

 • For the analysis of the time to AE onset/worsening, if the AE onset/worsening date is missing then the time to AE onset/worsening will be counted as 1 day.

